and up to 6 subjects. Dose escalation will be guided by an adaptive Bayesian logistic regression model (BLRM) following the dose escalation with overdose control (EWOC) principle. This design uses all accumulating toxicity data to assign enrolling subjects to doses that have a higher chance of targeted toxicity (close to the MTD), while controlling the risk of excessive toxicity. To further ensure safety, the safety findings of each cohort will be carefully reviewed by the Safety Review Committee (SRC) prior to dose escalation decisions for the subsequent dose cohort.

During Phase 1, if a subject is tolerating AFM24 without significant evidence of disease progression or AFM24-related toxicity, the subject may, beginning with Cycle 3 or a subsequent cycle, have the dose increased to a dose that has already been established as tolerable by the SRC, and with the agreement of the SRC. This intra-subject dose escalation may allow subjects a greater possibility of benefit from treatment with AFM24 than might be achieved at the starting dose in his/her assigned dose cohort.

Risks of the tumor biopsy (mandatory for the subjects in the dose escalation phase [Phase 1]) include pain and tenderness at the tumor biopsy site and potential bleeding complications, which will be minimized by inclusion of subjects who have at least 1 site of tumor that is accessible to biopsy and that is considered by the Investigator to be low risk and of sufficient size to undergo a biopsy procedure, and monitoring per institutional practice.

No reproductive toxicity or carcinogenicity studies have been conducted with AFM24 to date. Both women and men should be fully informed of the lack of reproductive toxicity testing. Women of childbearing potential and men must agree to use adequate contraception from 14 days prior to the first dose of study drug up to 120 days after the last dose of study drug. Women must have a negative pregnancy test within 7 days prior to first dose of AFM24. It is unknown whether the drug is excreted in human milk, and women who are breast feeding are excluded from the study.

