3.4.2 Definition of Dose-Limiting Toxicity (DLT)

Dose-limiting toxicity is defined as an AE or abnormal laboratory value assessed as unrelated to underlying disease, disease progression, inter-current illness, or concomitant medications, that occurs ≤ 28 days following the first dose of AFM24 (Cycle 1) and that meets any of the following criteria shown in Table 3. Clinically relevant toxicities will be evaluated according to the National Cancer Institute (NCI)/National Institutes of Health CTCAE v5.0. Subjects who experience a DLT during Cycle 1 must permanently discontinue AFM24.

Subjects must receive $\geq 80\%$ of their assigned AFM24 dose in Cycle 1 and complete the 28-day DLT observation period or have had a DLT within the first cycle of treatment to be considered evaluable for DLT.

For dose-escalation decisions, only DLTs occurring during Cycle 1 of treatment will be considered in the 2-parameter BLRM.

Table 3: Definition of Dose Limiting Toxicity

Toxicity	Any of the following criteria
Hematological ^a	\geq CTCAE Grade 4 neutropenia (ANC $<0.5 \times 10^9/L$) lasting for longer than 4 consecutive days
	Febrile neutropenia (ANC $<1.0 \times 10^9/L$ of any duration accompanied by fever $\geq 38.5^\circ C$ or systemic infection)
	CTCAE Grade 3 thrombocytopenia (platelets 25 to $<50 \times 10^9/L$) associated with bleeding
	CTCAE Grade 4 thrombocytopenia (platelets $<25 \times 10^9/L$)
	\geq CTCAE Grade 4 anemia that is considered to be treatment related
Non-hematological	
Any \geqCTCAE Grade 3 AE including, but not limited to:
 
• CTCAE Grade 3 infusion-related reaction/cytokine release syndrome not responsive to symptomatic treatment within 6 hours (ie, no improvement to Grade 2 or better within 6 hours with optimal medical management)• CTCAE Grade 4 infusion-related reaction/cytokine release syndrome• QTcF prolongation (>500 msec)

Toxicity	Any of the following criteria

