	
 CTCAE Grade 3 hypertension for >14 consecutive days despite optimal anti-hypertension therapy CTCAE Grade 4 hypertension ≥CTCAE Grade 3 total bilirubin (>3×ULN) ≥CTCAE Grade 3 ALT, AST, or ALP (>5×ULN) Subjects without hepatic metastasis: subjects fulfilling Hy's law criteria or 1.5 times increase from baseline value of total bilirubin for >2 weeks^b; Subjects with hepatic metastasis: 1.5 times increase from baseline value of total bilirubin for >2 weeks^b; ≥CTCAE Grade 3 vomiting or nausea for ≥72 hours despite optimal anti-emetic therapy; and/or ≥CTCAE Grade 3 diarrhea for ≥72 hours despite optimal anti-diarrhea treatment
	Any other ≥CTCAE Grade 3 AE not listed above, except for the exclusions noted below
	Inability to receive at least 3 of the scheduled doses of AFM24 in Cycle 1 due to treatment-related toxicity
	
Any other toxicity (irrespective of grade) that:
 
 Is greater than that at baseline and clinically significant and/or unacceptable and/or does not respond to supportive care and judged to be a DLT by the SRC; or Results in a disruption of AFM24 dosing for more than 2 weeks
Exceptions to DLT criteria ^c	Isolated laboratory changes of any grade without clinical sequelae or clinical significance with the exception of those laboratory changes outlined above
	CTCAE Grade 3 fever (in the absence of neutropenia) or fatigue that resolves to <Grade 3 within 72 hours
	CTCAE Grade 3 hypertension for ≤14 consecutive days
	CTCAE Grade 3 nausea, vomiting, diarrhea, or dehydration that resolves to <Grade 3 within 72 hours of initiating optimal supportive care treatment
	CTCAE Grade 3 infusion-related reaction/cytokine release syndrome responsive to symptomatic treatment within 6 hours (ie, improvement to Grade 2 or better within 6 hours with optimal medical management)

AE = adverse event; ALT = alanine aminotransferase; ALP = alkaline phosphatase; ANC = absolute neutrophil count; AST = aspartate aminotransferase; CTCAE = Common Terminology Criteria for Adverse Events; DLT = dose-limiting toxicity; NCI = National Cancer Institute; QTcF = corrected QT interval by Fridericia; SRC = Safety Review Committee; ULN = upper limit of normal.

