5.4 Dose Interruptions or Delays

AFM24 dosing delays may be permitted in the case of medical/surgical events or logistical reasons not related to study therapy (e.g., elective surgery, unrelated medical events, subject vacation and/or holidays). Subjects should re-commence study therapy within 3 weeks of the interruption, unless otherwise discussed and agreed with the Sponsor. Every effort should be made to avoid dose delays during the DLT observation period (Cycle 1 of the dose escalation phase).

Dose delays of up to 3 weeks (≤ 21 days between 2 consecutive doses) are allowed for subjects to recover from any AE and return to baseline or Grade ≤ 1 (except for fatigue or anorexia).

Subjects who do not recover from any AE and return to baseline or Grade ≤ 1 (except for fatigue or anorexia) within 3 weeks (≤ 21 days between 2 consecutive doses) must discontinue AFM24 permanently.

Please refer to APPENDIX A (Section 14.1) and APPENDIX B (Section 14.2) for more details of weekly and q2w AFM24 dosing schedules, respectively.

Weekly dosing schedule:

If the subject recovers from an AE and is able to continue study drug within 72 hours of the originally scheduled dosing day, then the subject should receive the delayed dose and continue treatment as per the original schedule, by not shifting any later doses. There should be at least 4 days without treatment before the subject receives the next dose. An example: if the subject has an AE on C1D15 and recovers in time and can receive the missed dose on C1D18, then the next dose for the subject is on C1D22.

If the subject does not recover from an AE within 72 hours, the missed dose(s) should be skipped and the subject should receive the next dose as per original schedule. An example: a missed dose on C2D1 and the subject recovered on C2D9, the next dose for this subject is on C2D15.

Every-2-weeks dosing schedule:

If the subject recovers from an AE and is able to continue study drug within 1 week from the original scheduled dosing day then the subject should receive the delayed dose and continue treatment as per the original schedule, by not shifting any later doses. There should be at least 7 days without treatment before the subject receives the next dose. An example: if the subject has an AE on C1D1 and recovers in time and can receive the missed dose latest on C1D8, then the next dose for the subject is on C1D15.

Further dose delays or skipping is not allowed for subjects to recover from any AE.

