7.2.12 Tumor Genomics and Tumor Biopsy

Blood samples for the assessment of tumor genomics from circulating tumor DNA will be taken as described in the Schedule of Pharmacokinetic, Pharmacodynamic, Immunogenicity,

and Translational Assessments (see APPENDIX A [Section 14.1] for weekly dosing schedule and APPENDIX B [Section 14.2] for q2w dosing schedule). Analysis will measure quantitatively the amount of circulating tumor DNA and a search will be done for known targetable tumor mutations (such as but not limited to known mutations in EGFR, anaplastic lymphoma kinase, BRAF genes). Full details of sample collection and handling of the sample will be described in the Lab Manual for the study.

For Phase 1 only: An initial tumor biopsy will be performed at Screening and 1 tumor biopsy will be performed during treatment with AFM24 on Day 24 of Cycle 1 (see SoA tables APPENDIX A [Section 14.1] for weekly dosing schedule and APPENDIX B [Section 14.2] for q2w dosing schedule). Tumor biopsies are mandatory for subjects in escalation phase (Phase 1). Tumor samples will be evaluated centrally to assess EGFR positivity of cancer cells, infiltrating NK cells and macrophages and their subpopulations, and additional markers.

For Phase 2a only: for diagnostic purposes, a tumor biopsy at pre-screening is needed for EGFR assessment if there is no archived tumor tissue available. Tumor biopsies for central lab analysis are not collected in the expansion phase.

Samples will be used only for purposes related to this research. Unused samples of subjects who separately consented to long-term storage will be stored up to maximum of 15 years or until the Sponsor has determined that specimens are no longer needed, and the decision has been made that none of the samples needs to be reanalyzed, whichever is sooner. In addition, samples can be destroyed at any time at the request of the subject.

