8.1 Adverse and Serious Adverse Events

8.1.1 Definition of Adverse Events

An AE is defined as any new untoward medical occurrence or worsening of a pre-existing medical condition in a subject or clinical investigation subject administered a medicinal product and which does not necessarily have a causal relationship with this treatment. An AE can therefore be any unfavorable and unintended sign (including a clinically significant abnormal laboratory finding, for example), symptom, or disease temporally associated with the use of a medicinal (investigational) product, whether considered related or unrelated to AFM24.

During clinical studies, AEs can be spontaneously reported or elicited during open-ended questioning, examination, or evaluation of a subject. To prevent reporting bias, subjects should not be questioned regarding the specific occurrence of 1 or more AEs. Adverse events include:

- Worsening (change in nature, severity, or frequency) of conditions present at the start of the study;
- Intercurrent illness;
- Drug interactions;
- Experiences related or possibly related to concomitant medications;
- Clinically significant abnormal laboratory values or shifts from baseline;
- Clinically significant abnormalities in physical examination, vital signs, weight, or ECG; and
- An accident or injury.
- Adverse events which are related to study procedures (for example a biopsy)

Adverse Events Expected Due to Disease Progression

The term “disease progression” alone should not be used when reporting AEs or SAEs, due to its lack of specificity. Rather, symptoms of disease progression should be reported. If death occurs as consequence of disease progression, this would be considered an outcome, and NOT an AE.

Example, a subject died due to a pulmonary hemorrhage secondary to tumor progression; an SAE report should be submitted with the event pulmonary hemorrhage notified as a Grade 5 (fatal) event.

Surgical procedures or other therapeutic interventions themselves are not AEs, but the condition for which the surgery/intervention is required is an AE and should be documented accordingly.

Planned surgical measures and the condition(s) leading to these measures are not AEs if the condition(s) was (were) known before the period of observation and did not worsen during study. In the latter case, the condition should be reported as medical history.

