- o. Urinalysis parameters include glucose, protein, bilirubin, ketones, blood, pH, specific gravity (microscopic examination when indicated), FSH (to confirm post-menopausal status [Screening], and human chorionic gonadotropin (female pre-menopausal subjects [Screening] (See [APPENDIX D](#), Section [14.4](#)).
- p. Coagulation may be assessed from the hematology sample.

- q. Tumor biopsy for central analysis is required for subjects in the dose escalation phase (Phase 1) only.
- r. +1 week: The second tumor biopsy will be performed on a non-dosing day during week 3 (+1 week).
- s. CT or MRI will be done at Screening and during the last week of cycles 2, 4, 6, 8, and every 3 cycles thereafter.
- t. During pre-screening, only AEs which are related to study procedures are to be recorded. AEs occurring after signing of the Main ICF but prior to the first dose of study drug should be recorded on the Medical History eCRF page (**Note:** any SAEs which are related to study procedures and occur during pre-screening and any SAEs that occur following signing the Main ICF and prior to the first dose of study drug will still be reported using the SAE form). Please also refer to Section 8.1.3 for detailed description.
- u. Concomitant medications administered after the Safety Follow-up visit should be recorded for SAEs which are considered related to study drug.

ADA = anti-drug antibodies; C = cycle; CT = computed tomography; ctDNA = circulating tumor DNA; D = day; ECG = electrocardiogram; ECOG PS = Eastern Cooperative Oncology Group Performance Status; EGFR = epidermal growth factor receptor; EOI = end of infusion; EOT = End of Treatment visit; FSH = follicle-stimulating hormone; HIV = human immunodeficiency virus; I/E = inclusion/exclusion; ICF = informed consent form; LT-FU = long term follow-up; MRI = magnetic resonance imaging; PD = pharmacodynamics; PK = pharmacokinetics; SCR = screening; S-FU = Safety Follow-up visit.

Table 12: Schedule of Pharmacokinetic, Pharmacodynamic, Immunogenicity, and Translational Assessments for Weekly AFM24 Dosing Regimen (Without Split Dosing) - For Phase 1

Sample	SCR	Cycle 1												
		D1			D3		D7	D8	D15	D22			D24	D28
		Pre	EOI ^a	+1h EOI ^a	+48h EOI ^a	+2h	+144h EOI ^a	Pre	Pre	Pre	EOI ^a	+1h EOI ^a	+48h EOI ^a	+144h EOI ^a
PK		X	X		X	X	X	X	X	X	X	X	X	X
ADA ^b		X					X	X	X					
CD16a RO	X				X					X			X	
PD (circulating lymphocytes)		X		X	X			X	X	X		X	X	
PD (cytokines) ^c		X	X		X			X	X	X	X		X	

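### The DLT definition does not exclude study procedures, so a Grade 3 or higher complication of the mandatory Phase 1 biopsy counts as a DLT; a loose footnote on biopsy timing adds a smaller problem

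*Protocol*

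**What the plan says.** **Biopsy timing.** Protocol section 7.2.12 makes the on-treatment biopsy mandatory in Phase 1: "1 tumor biopsy will be performed during treatment with AFM24 on Day 24 of Cycle 1". It refers to the schedule of assessments, where footnote r of Table 11 (Appendix A) reads "1 week: The second tumor biopsy will be performed on a non-dosing day during week 3 (+1 week". Section 1.8 lists among the biopsy risks "pain and tenderness at the tumor biopsy site and potential bleeding complications".

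**DLT definition.** Under protocol section 3.4.2 a DLT is an adverse event or abnormal laboratory value "assessed as unrelated to underlying disease, disease progression, inter-current illness, or concomitant medications", with onset no later than 28 days after the first dose, that meets a criterion in Table 3. One row of that table takes in any other event at or above "Grade 3 AE not listed above, except for the exclusions noted below". SAP 7.7.1 repeats the same four excluded causes and takes the DLT from the case report form. Protocol section 8.1.1 counts as adverse events "Adverse events which are related to study procedures (for example a biopsy", as an item separate from intercurrent illness.

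**Evaluability.** A subject without a DLT must receive at least 80% "of their assigned AFM24 dose in Cycle 1 and complete the 28-day DLT observation period". Section 5.4 adds, for weekly dosing: "If the subject does not recover from an AE within 72 hours, the missed dose(s) should be skipped".

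**The concern.** DLT incidence is the Phase 1 primary endpoint and the only outcome that updates the dose-escalation model (BLRM). The protocol orders an invasive procedure inside the DLT window, names bleeding as one of its risks, and counts its complications as adverse events. Yet the causes that take an event out of the DLT definition do not include study procedures. A complication of the needle can therefore enter the model as toxicity of the drug. Section 3.4.2 also requires the subject to stop AFM24 permanently.

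A second, smaller issue is that footnote r is looser than section 7.2.12. If it lets a site take the biopsy before the fourth dose, a modest complication could cost that dose and remove the subject from the dose-determining set.

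**Working it through.** **1. Is a Grade 3 or higher biopsy complication a DLT as written?**
- Timing: Day 24 is 23 days after the first dose, inside the 28-day limit.
- Excluded causes: disease, progression, intercurrent illness, concomitant medication. A biopsy bleed is none of these, and section 8.1.1 lists procedure events apart from intercurrent illness.
- Table 3: the row for other events of Grade 3 or higher applies. The exceptions list covers isolated laboratory changes, fever or fatigue, hypertension, gastrointestinal events and dehydration, and infusion reactions. It has no procedural item.
- Relatedness to AFM24 cannot be read in. The protocol writes it out where it is wanted: in the anemia row, in the missed-dose row, and in the section 3.4 rule that suspends accrual after Grade 4 or 5 events.

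The answer is yes, on any biopsy day, provided onset falls within the window.

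**2. What does one such DLT do to the dose?**

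Inputs: the model logit p(d) = log α + β·log(d/180) (section 9.3.4.1) and the Table 8 prior, with (log α, log β) normal, means -1.983 and -0.217, SDs 2.000 and 1.000, correlation 0. The posterior is proportional to the prior times the product of p^x(1-p)^(n-x) over doses, and was computed on a numerical grid. A dose is ruled out if P(DLT rate ≥ 33%) exceeds 0.25. The rows below all include 0/2 at 14 mg and 0/2 at 40 mg; the 360 mg rows also include 0/3 at 120 mg.

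| Table 19 scenario | Data at current dose | Dose assessed | P(overdose), Table 19 | Recomputed | Next dose |
|---|---|---|---|---|---|
| 8 | 0/3 at 120 mg | 360 mg | 0.245 | 0.236 | 360 mg |
| 9a | 1/3 at 120 mg | 120 mg | 0.159 | 0.166 | 120 mg |
| 12 | 0/3 at 360 mg | 1000 mg | 0.225 | 0.218 | 1000 mg |
| 13 | 1/3 at 360 mg | 360 mg | 0.280 | 0.280 | 200 mg |

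The protocol's figures reproduce to within 0.01. With 1/3 at 120 mg, even 200 mg is ruled out (0.365). With 1/3 at 360 mg, the current dose exceeds the limit, and 200 mg is allowed (0.058 recomputed, 0.063 in Table 19).

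**3. What does footnote r allow?**

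Doses fall on Days 1, 8, 15 and 22. If week 3 is Days 15-21 and one week is added, the non-dosing days are 16-21 and 23-28: 12 days, of which 6 precede the Day 22 dose. If the extra week is instead attached to Day 24, the allowed days are 24-28 and 30-31, none before Day 22. Day 24 fits both readings.

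**4. When is a subject lost?**

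Only the first reading matters here. Suppose a Grade 2 or lower complication after a Day 16-21 biopsy leads the investigator to hold the Day 22 dose, and it has not recovered within 72 hours. The dose is skipped, and 3/4 = 75%, below 80%. The missed-dose DLT row does not apply, because it needs fewer than three doses and treatment-related toxicity. The subject is not evaluable. In a cohort of three this leaves two, under the minimum of three in section 3.4, so a replacement is needed; in a cohort of four it is not.

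**5. How often?**

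The documents give no complication rate. Purely as an assumption, with a Grade 3 or higher rate r inside the window, the chance of at least one in a cohort of three is 1-(1-r)^3: 3% for r = 1%, 6% for 2%, 14% for 5%.

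**The case against.** Counting every Grade 3 or higher event unless a listed cause explains it is a cautious choice for a first-in-human trial, and bleeding at a biopsy site may partly reflect the drug, for instance through thrombocytopenia. That stands, and it is why any exclusion needs case review. It does not explain why intercurrent illness and concomitant medication are excluded while a protocol-mandated procedure is not.

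The SRC might set such an event aside in practice. Table 3 lets it add a DLT by judgment; nothing in the protocol or SAP lets it remove one. Its charter is not among the documents, so this cannot be settled.

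The lost-subject route is narrow. Inclusion criterion 9 requires a low-risk site, section 5.4 asks for every effort to avoid delays in the DLT period, holding a dose for a Grade 2 or lower event is generally elective, and a site following section 7.2.12 literally never meets the problem. All of this stands. The columns of Table 11 are also broken in the text available, so the cell carrying footnote r could not be checked.

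A reader might infer that one and the same complication could be a DLT, a lost subject or neither, depending on how a site reads the footnote. The documents do not support that. A Grade 3 or higher event inside the window is a DLT on any biopsy day, and a subject with a DLT is evaluable by definition. A Grade 2 or lower event is not a DLT under the Grade 3 criterion; timing decides only whether the subject is lost.

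**Conclusion.** The concern holds as two separate points of unequal weight. The main one is that the DLT definition, read as written, counts a Grade 3 or higher biopsy complication in the window as a DLT. The effect per event is large under the protocol's own scenarios: the next dose falls from 360 mg to 120 mg, or from 1000 mg to 200 mg. The lesser one is that footnote r can be read to allow a biopsy before the Day 22 dose, with a narrow route to losing an evaluable subject.

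The Table 19 contrasts show what any single DLT does; they say nothing about how often biopsies cause one. The documents report no biopsy complication and no DLT in 6 subjects at 480 mg, where a Phase 2 dose was chosen, and Phase 1 conduct is probably over. They do not support an inference that the dose selection was distorted. What remains is the final DLT table and dose-determining set in the study report. Severity: minor.

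**What to change.** 1. In protocol 3.4.2 and SAP 7.7.1, add study procedures, with biopsy as the example, to the excluded causes, unless the SRC judges that AFM24 contributed.
2. Align footnote r with section 7.2.12: Day 24, with a window of non-dosing days after the Day 22 dose and up to Day 28. That is Days 23-28, or Days 24-28 with split dosing.
3. For the study report, flag any DLT or missed Day 22 dose attributed to the biopsy. If a procedure-related DLT exists, repeat the DLT table and BLRM without it as a sensitivity analysis. If there is none, one sentence closes the question.

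The cost is a phrase in two definitions, one footnote and one flag. DLT listings (SAP 7.7.1) and reasons for dose delays (SAP 7.8.1) are already planned. Sites that used Days 16-21 would lose those days but keep six, or five with split dosing. The real downside is that a drug effect could be wrongly blamed on the biopsy; SRC review of each case limits this. If Phase 1 enrolment is complete, only the third item still has practical effect.
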